8.3.1 Method of Detecting Adverse Events and Serious Adverse Events

At each study visit, the participant will be queried on changes in his or her condition.

Care will be taken not to introduce bias when detecting AEs and/or SAEs. Open-ended and non-leading verbal questioning of the participant is the preferred method to inquire about AE occurrences.

The method of recording, evaluating, and assessing causality of AEs and SAEs and the procedures for completing and transmitting SAE reports are in [Appendix 4](#).

8.3.2 Follow-up of Adverse Events and Serious Adverse Events

After the initial AE/SAE report, the Investigator is required to proactively follow each participant at subsequent visits/contacts. All SAEs, and AESIs (as defined in Section 8.3.7), will be followed until resolution, stabilization, the event is otherwise explained, or the participant is lost to follow-up (as defined in Section 7.3). Reasonable attempts to obtain this information will be made and documented. It is also the Investigator's responsibility to ensure that any necessary additional therapeutic measures and follow-up procedures are performed. Further information on follow-up procedures is in [Appendix 4](#).

8.3.3 Regulatory Reporting Requirements for Serious Adverse Events

Prompt notification by the Investigator to the Sponsor of an SAE (particularly life-threatening and deaths) is essential so that legal obligations and ethical responsibilities towards the safety of participants and the safety of a study intervention under clinical investigation are met.

The Sponsor has a legal responsibility to notify both the local regulatory authority and other regulatory agencies about the safety of a study intervention under clinical investigation. The

Sponsor will comply with country-specific regulatory requirements relating to safety reporting to the regulatory authority, IRB/IEC, and Investigators.

Individual Case Safety Reports will be prepared for SUSARs according to local regulatory requirements and Sponsor policy and forwarded to Investigators within 15 days.

An Investigator or sub-investigator who receives an Individual Case Safety Report describing a SUSAR or other specific safety information (e.g., Emerging Safety Issue Report, summary or listing of SAEs/SUSARs) from the Sponsor will review the safety reports and confirm completion of this review. This information will be filed in the Investigator's Site File and the IRB/IEC will be notified, if appropriate, according to applicable local laws/regulations and site SOPs.

8.3.4 Pregnancy

- Details of all pregnancies in female participants will be collected after the start of study intervention and until the Safety Follow-up. Note: In this study, only women of nonchildbearing potential will be included.
- If a pregnancy is reported, the Investigator will record the pregnancy information on the appropriate form and submit it to the Sponsor within 24 hours of female participant pregnancy.
- While pregnancy itself is not considered to be an AE or SAE, any pregnancy complication or elective termination of a pregnancy will be reported as an AE or SAE. Adverse pregnancy outcomes (e.g., spontaneous abortion, fetal death, stillbirth, congenital anomalies, ectopic pregnancy) are considered and reported as SAEs. A spontaneous abortion (occurring at < 22 weeks gestational age) or stillbirth (occurring at > 22 weeks gestational age) is always considered to be an SAE and will be reported as such.
- The participant will be followed to determine the outcome of the pregnancy. The Investigator will collect follow-up information on the participant and the neonate, and the information will be forwarded to the Sponsor. Generally, follow-up will not be required for longer than 6 to 8 weeks beyond the estimated delivery date for a healthy newborn. In case of a congenital anomaly or other illness of the newborn, follow-up will continue until the illness has resolved or there is a definite outcome of the event.
- Any post study pregnancy related SAE considered reasonably related to the study intervention by the Investigator will be reported to the Sponsor as specified in Section 8.3.3. While the Investigator is not obligated to actively seek this information in former study participants, he or she may learn of an SAE through spontaneous reporting.
- Any female participant who becomes pregnant while participating in the study will discontinue study intervention or be withdrawn from the study.

8.3.5 Cardiovascular and Death Events

Not applicable.

8.3.6 Disease-Related Events and/or Disease-Related Outcomes Not Qualifying as AEs or SAEs

Not applicable.

8.3.7 Adverse Events of Special Interest

For this study, AESI(s) include only the following:

- Infections (serious, severe, and opportunistic, \geq Grade 3)

As per its mechanism of action, evobrutinib may impair B cell function which might lead to a decreased humoral immunity and consequently an increased risk of infection. Overall, in completed studies in participants the Medical Dictionary for Regulatory Activities SOC infection was one of the most reported SOCs (e.g., in the MS200527_0086 RMS study approximately 18% to 32% of participants treated with evobrutinib reported infection; a similar rate was reported in the placebo group in the 0 to 24 week period), the individual events were of low grade, mainly Grade 1, nonserious and did not lead to study intervention discontinuation. Treatment of infections must be prompt and done in accordance with local standard of care depending on considerations such as the nature and severity of the infection and participant's overall health status. Any Common Terminology Criteria for Adverse Events Grade ≥ 3 or SAEs of infection and opportunistic infection are considered as an AESI.

- Seizures

Seizures are more common in patients with MS than in the general population, occurring in 2% to 3% of MS patients (Poser 2003). Convulsions were observed in early studies of evobrutinib in dogs, however the plasma concentration of evobrutinib was approximately 140-fold greater than it is predicted for the dose used in this study. One participant with RMS with significant brain lesion load reported seizure of unclear clinical picture. The PK data for this participant did not exceed the expected values and was similar to other participants in the study. Anticonvulsant therapy was started, and the participant continued treatment with evobrutinib with no reoccurrence. The Investigator did not consider the event to be related to evobrutinib. No event of convolution/seizure was reported in other indications. Evobrutinib has been administered to approximately 800 patients with MS, rheumatoid arthritis and systemic lupus erythematosus. Moreover, an electroencephalogram study in healthy volunteers did not show an epileptogenic potential for evobrutinib. Any type of seizures/epilepsy of any grade or its consequences are classified as AESIs.

- Elevated lipase, elevated amylase, pancreatitis

Asymptomatic elevations in amylase or lipase or both in participants treated with evobrutinib have been observed at a variety of time points and reported as TEAEs or noted as laboratory abnormalities. In RMS Study MS200527_0086, the incidence of TEAEs of lipase increased was slightly higher in evobrutinib 75 mg once daily and 75 mg twice daily arms (5 [9.4%] and 5 [9.3%], respectively) when compared to other arms (approximately between 4% to 6%). However, shifts from Baseline to highest grade on treatment were similar across all treatment arms for both amylase and lipase. In evobrutinib studies in other indications and in healthy participants, the incidence of TEAEs of increased amylase or lipase, or both was infrequent and

no clinically meaningful differences were observed across treatment arms. Any elevation of $> 2 \times$ ULN of lipase or amylase and any type of pancreatitis are classified as AESIs.

- Liver related events

The elevations of transaminases observed in participants treated with evobrutinib were frequent, asymptomatic, and reversible on discontinuation of evobrutinib. The mechanism is unknown.

Evobrutinib liver AESIs will include transaminases ($> 3 \times$ ULN), bilirubin elevations ($> 1.5 \times$ ULN), biological Hy's Law cases based on laboratory data, any type of acute or chronic hepatitis (any grade), suspected drug-induced liver injury, acute or chronic hepatic failure, fibrosis, cirrhosis, and other liver damage-related conditions.

AESIs have to be reported immediately (within 24 hours). For reporting of AESIs, see [Appendix 4](#).

8.4 Pharmacokinetics

- The following PK parameters will be calculated, when appropriate: PK parameters will be calculated for all analytes and unless otherwise noted.

Symbol	Definition
$AUC_{0-\infty}$	The AUC from time zero (= dosing time) up to infinity with extrapolation of the terminal phase.
$AUC_{0-t_{last}}$	The AUC from time zero (= dosing time) to the time of the last quantifiable concentration (t_{last}).
C_{max}	Maximum observed concentration.
t_{max}	The time to reach the C_{max} in a dosing interval.
$t_{1/2}$	The terminal half-life.
CL/F	The apparent total body clearance following extravascular administration (EE, NET, CCI [REDACTED] only).
V_z/F	The apparent volume of distribution during the terminal phase following extravascular administration (EE, NET, CCI [REDACTED] only).
CCI [REDACTED]	[REDACTED]
[REDACTED]	[REDACTED]

- Whole blood samples of approximately 4 mL for measurement of plasma concentrations of EE/NET and 3 mL for measurement of **CCI** [REDACTED] and **CCI** [REDACTED] will be collected. Collection times are specified in the Schedule of Assessments (see Section 1.3).
- EE/NET samples will be collected starting on Day 1 and Day 15 with timepoints predose through 72 hours postdose. On Day 4, the 72 hours postdose sample will be collected prior to evobrutinib dosing.

CCI [REDACTED]

- The actual date and time (24-hour clock time) of each sample will be recorded to calculate actual time elapsed since the prior dose administration.

- The quantification of EE/NET and evobrutinib in plasma will be performed using a validated assay method. CCI [REDACTED]
- Remaining samples collected for analyses of EE/NET and CCI [REDACTED] concentrations may also be used to evaluate safety or efficacy aspects related to concerns arising during or after the study. Additionally, remaining plasma samples may be used for investigation of other CCI [REDACTED].
- Details on processes for collection and handling of these samples are in the Laboratory Manual. Retention time and possible analyses of samples after the end of study are specified in the respective ICF.

The accepted time deviations from planned PK sampling times that will not be considered a protocol violation are listed below. Any deviation from these time windows requires a comment in the eCRF and may be discussed in the data review meeting.

Procedure	Time Point (Relative Time)	Window Allowance
Pharmacokinetics	Predose	Day 1: - 60 min Day 4: - 60 min Day 15: - 5 min
	0.25 to 1 hours postdose	± 2 min
	> 1 to 12 hours postdose	± 5 min
	> 12 to 24 hours postdose	± 15 min
	> 24 to 72 hours postdose	± 30 min

CCI

8.6 Biomarkers

Not applicable.

8.7 Immunogenicity Assessments

Not applicable.

8.8 Health Economics

Not applicable.

9 Statistical Considerations

[figure not shown]
All planned analyses defined in this protocol will be described in the IAP that will be finalized before the database lock.

Changes in the conduct of the study or planned analyses, if any, will be reported in the appropriate section of the IAP and in the CSR.

9.1 Statistical Hypotheses

The statistical analysis of study data will be purely descriptive; no hypothesis tests will be performed. A definition of primary and secondary objectives and endpoints can be found in Section 3.

CCI

CCI

CCI

9.3 Analyses Sets

The analysis sets are specified below.

The final decision to exclude participants from any analysis population will be made during a data review meeting prior to database lock.

Table 3 Analysis Sets

Analysis Set	Description
Screening (SCR)	All participants, who provided informed consent, regardless of the participant's enrollment and study intervention status in the study.
Safety (SAF)	All participants, who were administered any dose of any study intervention. Analyses will consider participants as treated.
Pharmacokinetic (PK)	
The PK Analysis Set is a subset of the SAF, and the PK population will include all participants:
 
Who have completed the study without any relevant protocol deviations and factors likely to affect the comparability of PK results.With adequate study intervention compliance.With evaluable PK data, i.e., no missing values for primary endpoints at each PK profile/assessment day (Day 1, Day 15). 
If participants received prohibited concomitant therapy or medicines, as specified in Section 6.8, they will be excluded from the PK population.
 
All PK analyses will be based on this analysis set.

PK = Pharmacokinetic; SAF = Safety; SCR = Screening.

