8.1 Definition of Analysis Sets

Analysis Set	Description
SCR	All participants, who provided informed consent, regardless of the participant's enrollment and study intervention status in the study.
SAF	All participants, who were administered any dose of any study intervention. Analyses will consider participants as treated.
PK	
The PK Analysis Set is a subset of the SAF, and the PK population will include all participants:
 
• Who have completed the study without any relevant protocol deviations and factors likely to affect the comparability of PK results.• With adequate study intervention compliance.• With evaluable PK data, i.e., no missing values for primary endpoints at each PK profile/assessment day (Day 1, Day 15). 
If participants received prohibited concomitant therapy or medicines, as specified in Section 6.8 in the CSP, they will be excluded from the PK population.
 
All PK analyses will be based on this analysis set.

PK=pharmacokinetics; SAF=safety; SCR=Screening.

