10.2 Protocol Deviations / Exclusion from Analysis Sets

10.2.1 Important Protocol Deviations

Listings of important protocol deviations will be provided including the date and relative day in relation to dosing in the relevant period. A distinction will be made between important protocol deviations due to COVID-19 versus not due to COVID-19. The respective important protocol deviations will be flagged accordingly.

Important protocol deviations or important events that might influence PK include, but may not be limited to the following:

- Adverse events, diarrhea etc. (these instances will be discussed on a case-by case basis)
- Vomiting after administration following oral dosing (these instances will be discussed in alignment with applicable regulatory guidelines on a case-by-case basis)
- Sample processing errors that may lead to inaccurate bioanalytical results
- Inaccurate dosing or dosing errors (e.g., dose administration delayed, dose change or missed doses)
- Predose or trough sample collected after the actual dosing
- Non-compliance with food and drink requirements (e.g., non-fasted, incomplete meal consumption, caffeine intake)
- Concomitant medication, vitamins, dietary or herbal supplements

Should one or more of these events be available at the Data Review Meeting, its implication for PK evaluation will be discussed and agreed amongst relevant study team members (e.g., Sponsor Clinical Pharmacology/Biostatistics/Clinical Pharmacokinetics & Pharmacodynamics team representative). Appropriate action will be taken such as flagging individual values to be excluded from analysis.

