16.1.4 General Specifications for PK Concentration and PK Parameter Data

Predose samples that occur before the first drug administration will be assigned a time of 0 hours, as if the sample had been taken simultaneously with the study intervention administration. Same applies to the predose sample after multiple doses.

Predose or trough samples which have been taken after the subsequent dosing will be reported as a protocol deviation. The resulting concentrations will be included in concentration listings but excluded from descriptive statistics of concentrations and from PK parameter estimation.

Values BLQ will be taken as zero for summary statistics of PK concentration data, PK parameter estimation (e.g., AUC) and for graphical presentations.

Missing concentrations (e.g., no sample, insufficient sample volume for analysis, no result or result not valid) will be reported generally as “N.R.”. A participant who withdraws prior to the last planned observation will be included in the analyses up to the time of discontinuation if still included in the PK analysis set.

If samples are collected outside of 10% of the PK sampling time windows defined in the CSP in Section 8.4, these will be included in the PK parameter estimation (NCA) but will be excluded from the concentration summary and mean/median concentration plots.

PK concentrations which are erroneous due to a sampling processing or analytical error (as documented in the bioanalytical report) may be excluded from the PK analysis if agreed by the Sponsor. In this case the rationale for exclusion will be provided in the CSR. Any other PK concentrations that appear implausible to the Clinical Pharmacologist/Clinical PK/PD Scientist will not be excluded from the analysis. Any implausible data will be documented in the CSR.

If important protocol deviations occurred likely to affect the PK profile of participants as specified in Section 10.2.1, the impacted concentrations and PK parameters will be excluded from summary statistics and further statistical evaluation.

Any PK concentrations or PK parameters excluded from summary statistics will be included in participants listings and flagged; a reason for exclusion will be detailed in the CSR (e.g., a footnote or a table of exclusions). Any flags will be included in the study specific CDISC data sets.

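### Do the participant-level and value-level exclusion rules leave the PK Analysis Set open to more than one construction?

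*Protocol*

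**What the plan says.** Protocol 9.3 and SAP 8.1 define a single PK Analysis Set and base every PK analysis on it. Four conditions work at the level of the participant:

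- **Completion and deviations.** Members are those "Who have completed the study without any relevant protocol deviations and factors likely to affect the comparability of PK results".
- **Compliance.** Study intervention compliance must be adequate.
- **Evaluability.** The SAP requires "no missing values for primary endpoints at each PK profile/assessment day (Day 1, Day 15").
- **Prohibited medicines.** "If participants received prohibited concomitant therapy or medicines, as specified in Section 6.8, they will be excluded from the PK population".

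On timing, Protocol 9.3 says: "The final decision to exclude participants from any analysis population will be made during a data review meeting prior to database lock".

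Two later SAP sections deal with overlapping events. SAP 10.2.1 lists deviations and events that might influence PK, among them "Concomitant medication, vitamins, dietary or herbal supplements". It continues: "Should one or more of these events be available at the Data Review Meeting, its implication for PK evaluation will be discussed and agreed", and then: "Appropriate action will be taken such as flagging individual values to be excluded from analysis". SAP 16.1.4 begins: "If important protocol deviations occurred likely to affect the PK profile of participants as specified in Section 10.2.1, the impacted concentrations and PK parameters", and says that these are left out of summary statistics and further evaluation. SAP 10.2.2 provides for listing the reasons when a participant is excluded from the set, and separately when a concentration is excluded.

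**The concern.** The triggers in SAP 8.1 and SAP 16.1.4 are nearly the same: a deviation likely to affect comparability of PK results, and a deviation likely to affect the PK profile. The first removes the participant and the second removes values. Vitamins and herbal products are prohibited by Protocol 6.8.3, which points to exclusion of the participant, yet they also appear on the SAP 10.2.1 discussion list. No sentence says which rule comes first.

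Medicines given under Protocol 6.8.2 are a second loose end. Protocol 6.8.3 exempts them from the general prohibition but does not repeat the exemption for CYP3A4/5 inhibitors and inducers, and 6.8.2 accepts that emergency use may be a protocol deviation.

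The third point is timing. Several criteria need judgement, the study is open-label, and no passage says that EE/NET concentrations are withheld from the people applying them.

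At stake is whether two teams would build the same set of at most 20 participants, and whether membership could be influenced by the results.

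**Working it through.** **Reading the sections in order**

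1. *Membership comes first.* SAP 16.1 performs all PK statistics on the PK Analysis Set, so the exclusions in 16.1.4 act on its members. Section 16.1.4 uses this order itself: withdrawn participants contribute data only if they are still in the set.
2. *Prohibited medicine.* Protocol 9.3 and SAP 8.1 make exclusion mandatory. Protocol 7.2 also lists use of nonpermitted medication among the reasons a participant must be withdrawn, and a withdrawn participant has not completed the study. (Protocol 7.1 applies a clinical-relevance test to the same event, but for stopping study intervention. Membership of the set does not depend on it.) Discussion under SAP 10.2.1 does not cancel a mandatory rule. Its list also covers permitted medication such as ibuprofen, and its action is only an example.
3. *Value removed under SAP 16.1.4.* If the removed value is a primary parameter, the natural reading is that it is missing for the both-days rule in SAP 8.1, and the participant leaves the set. If it is a single concentration and the parameters can still be derived, she stays.
4. *Medicines under Protocol 6.8.2.* Protocol 7.2 again allows medicines needed for the participant's wellbeing. The unclear case is an emergency CYP3A4/5 inhibitor or inducer. Protocol 2.2 says EE and NET are CYP3A4 substrates, so such use would be judged under the comparability criterion whether or not it counts as prohibited.
5. *Timing.* Exclusions are final before lock (Protocol 9.3). Statistical analysis waits for corrected and checked data (Protocol 9.4), and final analyses follow lock (Protocol 9.4.4, SAP 6). SAP 16.1.4 bars exclusion for implausibility alone. SAP 16.1.5.1 keeps parameters flagged for poor terminal-phase fit in the outputs.

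**Size of the effect**

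The plan gives no figure to reproduce, and Protocol 9.2 is redacted. Inputs are n = 20 (the maximum in Protocol 1.1), a 90% CI (Protocol 9.4.3.1), and an assumed within-subject CV of 15%, 20% or 30%. On the log scale s_w = √ln(1 + CV²), and the Day 15 minus Day 1 difference has SD = √2 × s_w, which is 0.211, 0.280 or 0.415.

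| Quantity | Formula | CV 15% | CV 20% | CV 30% |
|---|---|---|---|---|
| 90% CI factor, n = 20 | exp(1.729 × SD/√20) | 1.085 | 1.114 | 1.174 |
| 90% CI factor, n = 19 | exp(1.734 × SD/√19) | 1.088 | 1.118 | 1.180 |
| Dropping one unaffected participant, 1 SD of log-ratio change | SD/√(20 × 19) | 0.0108 | 0.0144 | 0.0213 |
| Two arguable cases, higher ratio dropped: multiplier (coverage) | simulation | 0.994 (0.90) | 0.992 (0.90) | 0.988 (0.90) |
| Four arguable cases, two highest dropped: multiplier (coverage) | simulation | 0.985 (0.89) | 0.979 (0.89) | 0.970 (0.89) |

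The simulations use 200,000 sets of 20 log-ratios with a true ratio of 1.

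A participant kept in the set although her own ratio was altered by a factor f moves the overall ratio by f^(1/20). For f = 0.7 this is 0.982, and for f = 1.3 it is 1.013. For the more extreme f = 0.5 and f = 2.0 it is 0.966 and 1.035.

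**The case for a change.** The best case for a change is that the order above is inferred. No passage says that a parameter excluded under SAP 16.1.4 counts as missing under SAP 8.1. A literal reader could therefore drop one EE value and leave the participant in every NET comparison. The set is small, withdrawals are not replaced (Protocol 7.2), and no analysis in an alternative set is planned. The only sensitivity analysis, in SAP 16.1.5.1, is optional and concerns terminal-phase flags.

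On timing, whether a primary parameter exists must be known to settle the set. Either the parameters are derived before the meeting and could be seen there, or evaluability cannot be fully settled at it. Removal of erroneous concentrations needs only sponsor agreement, with no stated time.

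These observations are correct as far as they go. The precedence is not written out, the status of some 6.8.2 medicines is unclear, and release of concentrations is not addressed. They do not show a contradiction that would lead an analyst to a wrong set. It would also be too strong to say that nothing restrains late decisions, because participant exclusions are fixed before lock and the ratios are due after it. That values would be shown to those deciding is an inference from silence. A signed two-step meeting and a supportive analysis in all evaluable participants are reasonable preferences, but neither corrects an error.

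**Conclusion.** No change is needed. Followed as written, the plan gives a sound PK Analysis Set: mandatory exclusions first, value exclusions among members, and removal of anyone left without a primary parameter on either day. What is missing is detail that a competent team will fill in the same way.

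The room for judgement is narrow. Participants are resident from Day -1 to Day 18 (Protocol 1.1), dosing is supervised with mouth checks (Protocol 6.4), off-window and late predose samples have fixed handling (SAP 16.1.4), and exclusion reasons are listed (SAP 10.2.2). Four arguable cases among 20 participants is a stress test that nothing in the documents suggests. Even then the ratio falls by 1.5% to 3.0% and coverage of the 90% CI by about one percentage point, while the upper limit lies 8.5% to 17.4% above the estimate. The analysis is described as purely descriptive, with no hypothesis tests (Protocol 9.1), so no formal test decision turns on such a shift.

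The sizes rest on the assumed CVs and on all 20 participants being dosed and evaluable. The reading rests on treating an excluded primary parameter as missing. If the SAP is revised for another reason, a sentence on precedence and one on medicines given under Protocol 6.8.2 would be a harmless courtesy.
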